11.3.3. Reporting Standards for Pharmacokinetics

Pharmacokinetic Concentration Data	
Descriptive Summary Statistics, Graphical Displays and Listings	
Refer to IDSL PK Display Standards.
 
Refer to IDSL Statistical Principle 6.06.1.
 
For continuous data:
 
 NQs at the beginning of a participant profile (i.e., before the first incidence of a measurable concentration) are deemed to be 0 as it is assumed that in this circumstance no drug is yet measurable in the blood. For NQs at the end of the participant profile (i.e., after the last incidence of a measurable concentration): 
 For individual plots and PK analyses these are dropped (set to missing) as they do not provide any useful information (and can erroneously indicate that absolutely no drug is present) For summary statistics, these are set to 0 (to avoid skewing of the summary statistics) Individual NQs which fall between two measurable concentrations are set to missing (individual values of this nature are assumed to be an anomaly). 
If two or more NQ values occur in succession between measurable concentrations, the profile will be deemed to have terminated at the last measurable concentration prior to these NQs. For the purpose of individual participant plots, these NQs will be set to 0, and the subsequent measurable concentrations will be retained. For the derivation of PK parameters, these NQs and any subsequent measurable concentrations will be omitted (set to missing).
 
Note: Concentration values will be imputed as per GUI_51487 for descriptive summary statistics/analysis and summarized graphical displays only.

Pharmacokinetic Parameter Data	
Descriptive Summary Statistics, Graphical Displays, and Listings	N, n, arithmetic mean, 95% CI of arithmetic mean, geometric mean, 95% CI of geometric mean, SD, SD of logged data CV (%), and between-subject geometric CVb (%) will be reported. $CV_b (\%) = \sqrt{(\exp(SD^2) - 1)} * 100$ (SD = SD of Ln-Transformed data)
Parameters Not Being Ln-Transformed	Tmax, λz , λz lower, λz upper, and λz no. of points.
Parameters Not Being Summarized	λz , λz lower, λz upper, and λz no. of points.
Listings	Include the first point, last point and number of points used in the determination of λz and $Rsq_{adjusted}$ for listings.

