4.3. Justification for Dose

The therapeutic dose range of GSK3640254 being studied in HIV-1 infected adults is 100 to 200 mg (Study 208379, GSK Document Number 2019N399207_03). The dose of 150 mg GSK3640254 was selected for this study as this is below the maximum projected clinically therapeutic dose of GSK3640254. The highest GSK3640254 dose given with a moderate fat and calorie meal was 400 mg. The high fat and calorie meal may increase BA compared with moderate fat and calorie meal but will be below 400 mg SD dosed with moderate fat and calorie meal. The FDC of 150 mg GSK3640254 + 50 mg DTG strength is the starting dose that is a reasonable estimate of the GSK3640254 dose, based on current data. Furthermore, coadministration of DTG (50 mg) and GSK3640254 (200 mg) resulted in no clinically meaningful difference in the steady-state systemic exposure of GSK3640254 compared to GSK3640254 administered alone with geometric least squares mean ratios of 1.04, 0.991, and 0.996 for AUC(0- τ), Cmax, and C τ , respectively [GSK Document Number 2019N399318_00]. The apparent terminal phase half-life (t_{1/2}) of GSK3640254 was approximately 22 hours in the MAD portion of Study 207187 at the 200-mg dose [GSK document number 2020N430256_00]. To ensure adequate washout, there will be at least 7 days between each dose of study intervention, with an allowance window of 4 hours (i.e., 7 days minus 4 hours) to allow flexibility in scheduling participants for dosing at the clinic.

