7.1.1.2. Derived Pharmacokinetic Parameters

Pharmacokinetic parameters will be calculated by standard non-compartmental analysis according to current working practices and using the currently supported version of WinNonlin (8.0 or higher). All calculations of non-compartmental parameters will be based on actual sampling times. Pharmacokinetic parameters listed will be determined from the plasma concentration-time data, as data permit. Participants who experience emesis at or before 2 times median Tmax or participants whose pre-dose concentrations are >5% of their Cmax value for the given treatment will be excluded from the calculation of summary statistics and statistical analysis for the respective treatment.

Parameter	Parameter Description
AUC(0-∞)	Area under the plasma concentration-time curve from time 0 extrapolated to infinity, to be calculated using the linear trapezoidal rule for each incremental trapezoid and the log trapezoidal rule for each decremental trapezoid.
AUC(0-t)	Area under the plasma concentration-time curve from time 0 to the last quantifiable concentration, to be calculated using the linear trapezoidal rule for each incremental trapezoid and the log trapezoidal rule for each decremental trapezoid.
Cmax	Maximum observed concentration, determined directly from the concentration-time data.

NOTES:

- Additional parameters may be included as required.

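### The two-NQ termination rule in SAP 11.3.3 is not limited to the post-peak phase, so in a rare case a trace pre-dose residual plus an absorption lag would discard a sound dosing profile (minor)

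*SAP*

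**What the plan says.** SAP 11.3.3 (Reporting Standards for Pharmacokinetics) has four rules for NQ values:

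- **Leading NQs** are set to 0, but only those "before the first incidence of a measurable concentration".
- **Trailing NQs** are dropped for PK analyses.
- **A single embedded NQ** does no harm: "Individual NQs which fall between two measurable concentrations are set to missing" and the profile continues.
- **Two or more embedded NQs** end the profile. The trigger is "If two or more NQ values occur in succession between measurable concentrations", and the result is that "the profile will be deemed to have terminated at the last measurable concentration prior to these NQs". For PK parameters, those NQs and all later concentrations become missing. For individual plots the later concentrations are kept.

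A closing note refers to an internal guide for imputing concentrations, but restricts it to descriptive summaries or analysis and summarized displays. It does not reach parameter derivation.

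SAP 7.1.1.2 handles carryover separately: "participants whose pre-dose concentrations are >5% of their Cmax value for the given treatment will be excluded" from the summary statistics and statistical analysis for that treatment. A measurable pre-dose value of up to 5% of Cmax is therefore meant to stay in.

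Protocol 4.3 allows a minimum interval of 7 days less 4 hours between doses and reports that the GSK3640254 half-life "was approximately 22 hours in the MAD portion of Study 207187 at the 200-mg dose". It gives 14 h for DTG. Both schedules of activities sample pre-dose and then at 0.5, 1, 1.5 h and on to 96 h. SAP 7.2.1.2 lists Tlag as a derived parameter.

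**The concern.** A rule that stops a profile at consecutive NQs is sensible in the tail, where an isolated late measurable value is probably noise. As written, it also applies at the front. If the pre-dose sample is measurable, it is itself the first measurable concentration, so the leading-NQ rule no longer applies to the samples after it. NQs at 0.5 h and 1 h then lie between measurable values, the termination rule is met, and the whole absorption, peak and elimination curve is set to missing for derivation.

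All three primary parameters depend on that derivation. The affected profile would be a valid one that the 5% carryover rule is designed to retain. Without a written rule, someone would have to choose between losing it and rescuing it after seeing the data. According to SAP 2.1, the clinical pharmacology team doing this work is not blinded to treatment.

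**Working it through.** **1. The plan's own precision figure.** Protocol 9.2.1 gives a log-scale 90% CI half-width of 0.179 for GSK3640254 at N = 14 and CVw 27.2%. Half-width = t(0.95, n−1) × √ln(1 + CVw²) × √(2/n) = 1.771 × 0.2672 × √(2/14) = 0.179, which reproduces it.

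**2. Residual at the next dose.** The minimum interval is 168 − 4 = 164 h.
- GSK3640254: 164/22 = 7.45 half-lives; 2^(−164/22) = 0.57% of the starting level.
- DTG: 164/14 = 11.7 half-lives; 2^(−164/14) = 0.03%.

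Both are far under 5%, so SAP 7.1.1.2 would keep such profiles. The case is more plausible for GSK3640254.

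**3. The four rules applied literally.** This used a one-compartment oral profile on the protocol's sampling times with linear-up/log-down AUC. Assumed values, not in the documents and in arbitrary concentration units: LLOQ 4, Cmax about 700, pre-dose 4.03 (0.57% of Cmax), ka 0.5/h.

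| Lag (h) | NQs after pre-dose | Usable points | Cmax | AUC(0-t) |
|---|---|---|---|---|
| 0 | 0 | 18 | 703 | 25,464 |
| 0.75 | 1 | 17 | 703 | 25,553 |
| 1.0 | 2 | 1 | 4.03 | 0 |
| 1.25 | 2 | 1 | 4.03 | 0 |

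With one usable point, AUC(0-t) is 0 and cannot be log-transformed, and AUC(0-∞) cannot be estimated. If termination is confined to samples after Tmax and the pre-absorption NQs are set to 0, the 1.0 h lag profile returns to 18 points, Cmax 703 and AUC(0-t) about 25,600. A pre-dose residual of 1.5 times the LLOQ stays measurable throughout and never triggers the rule.

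**4. How close to the LLOQ the residual must be.** At a 22 h half-life the level falls by 1 − 2^(−0.5/22) = 1.6% in 0.5 h and 1 − 2^(−1/22) = 3.1% in 1 h. Without assay noise, the pre-dose value must lie within about 1.6% above the LLOQ. With an assumed assay CV of 5 to 20% and a lag of at least 1 h, the chance of measurable, NQ, NQ is about 15 to 23% if the true residual equals the LLOQ, at most about 4% at 1.2 times, and about 0 at 1.5 times.

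**5. Chance per profile when residuals vary between participants.** Assumed: lognormal residual with log-SD 0.4 to 0.7, assay CV 10 to 20%, decay at 22 h, and a lag of at least 1 h in every profile.

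| Median residual / LLOQ | Chance of the pattern |
|---|---|
| 0.1 | about 0 |
| 0.25 | up to 0.6% |
| 0.5 to 2 | about 0.7 to 5.7% |
| 3 | up to 0.9% |
| 5 | up to 0.22% |
| 10 | about 0 |

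**6. Consequence of a loss.** If whole participants were lost, the same formula gives 0.187 at n = 13 and 0.196 at n = 12, against 0.179 at 14. If instead one collapsed Cmax were kept among 14 test-treatment profiles, the geometric mean ratio would be multiplied by exp[ln(4.03/700)/14] = exp(−5.157/14) = 0.69.

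**The case against.** The strongest reply accepts the wording and disputes its importance.

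- **Frequency rests on assumptions.** The LLOQ, assay CV, spread of residuals and lag distribution are not in the documents. Planning to calculate Tlag does not show that it reaches 1 h. This stands. A reader might multiply 0.7 to 5.7% by the 36 Period 2 and 3 profiles of Part 1 (18 × 2) and expect about 0.3 to 2 losses. That would require every profile to lag at least 1 h and the median residual to lie near the LLOQ. With 14 evaluable participants the count is 28, not 36.
- **Exclusion under the 5% rule.** A reader might infer that the truncated Cmax equals the pre-dose value, so the ratio is 100% and the participant is automatically excluded for that treatment. The SAP does not say whether the check uses the truncated or the full Cmax. SAP 7.1.1.2 takes Cmax directly from the concentration-time data, which could mean either. This is an ambiguity, not an established exclusion.
- **Bias between treatments.** A reader might infer that losses would fall unevenly because lag may differ by formulation or meal. The documents give no lag data. In ABC/BCA/CAB and DE/ED each treatment appears once in every period, so loss tied to later periods alone is balanced. Differential loss is possible but not shown.
- **It would be noticed.** Individual plots keep the later concentrations, concentrations are listed, SAP 11.5.2 requires exclusions to be documented, and SAP 7.1.4.1 limits the analysis to well-defined profiles. This makes an unnoticed loss unlikely. None of it restores the data or says how the profile should be handled.
- **Impact is small.** One analyte in one participant-period is affected, no formal hypothesis is tested, and the mixed model keeps the other periods where the data allow. This stands.

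**Conclusion.** The point holds as a minor drafting defect. On its wording, SAP 11.3.3 gives a wrong result for a profile that SAP 7.1.1.2 intends to keep, and no other NQ rule covers the case. When it occurs, AUC(0-t), AUC(0-∞) and Cmax are lost or meaningless for that analyte and period. It can occur only in Period 2 or 3, mainly for GSK3640254.

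It should be rare: it needs a residual close to the LLOQ and NQs at both 0.5 h and 1 h. The percentages above depend on assumed assay and variability inputs and on a lag of at least 1 h in every profile, so they are conditional rates, not forecasts. Even the loss of a whole participant would move the GSK3640254 half-width only from 0.179 to about 0.187.

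**What to change.** Add to SAP 11.3.3, before any parameters are derived:

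> The two-NQ termination rule applies only to NQs after the observed post-dose Tmax. NQs after a measurable pre-dose value and before the first measurable post-dose concentration are set to 0 and the post-dose profile is retained. Successive NQs between the first measurable post-dose concentration and Tmax are set to missing and the profile is retained. The >5% pre-dose check uses the Cmax of the full post-dose profile.

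The third sentence is needed because confining termination to the period after Tmax would otherwise leave successive NQs on the rising limb without a rule. The fourth settles the order of operations. The cost is a few sentences in the SAP and the matching derivation step. No new data are needed, and the tail rule is unchanged.

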11.4. Appendix 4: Derived and Transformed Data

11.4.1. General

Multiple Measurements at One Analysis Time Point

 Mean of the measurements will be calculated and used in any derivation of summary statistics but if listed, all data will be presented. The worst finding/interpretation associated with multiple measurements as the finding/interpretation for that time point. Participants having both High and Low values for Normal Ranges at any post-baseline visit for safety parameters will be counted in both the High and Low categories of “Any visit post-baseline” row of related summary tables. This will also be applicable to relevant Potential Clinical Importance summary tables.
Study Day

 Calculated as the number of days from Dose Date on Period 1 Day 1: 
 Assessment Date = Missing → Study Day = Missing Assessment Date < Dose Date on Period 1 Day 1 → Study Day = Assessment Date – Dose Date on Period 1 Day 1 Assessment Date >= Dose Date on Period 1 Day 1 → Study Day = Assessment Date – Dose Date on Period 1 Day 1 + 1
Period Day

 Calculated as the number of days from First Dose Date for the respective period: 
 Assessment Date = Missing → Period Day = Missing Assessment Date < Dose Date on Period 1 Day 1 → Period Day = Assessment Date – Dose Date on Period 1 Day 1 Dose Date on Period 1 Day 1 <= Assessment Date < Dose Date on Period 2 Day 1 → Period Day = Assessment Date – Dose Date on Period 1 Day 1 + 1 Dose Date on Period 2 Day 1 <= Assessment Date < Dose Date on Period 3 Day 1 → Period Day = Assessment Date – Dose Date on Period 2 Day 1 + 1 Assessment Date >= Dose Date on Period 3 Day 1 → Period Day = Assessment Date – Dose Date on Period 3 Day 1 + 1

11.4.2. Study Population

Age

 GSK standard IDSL algorithms will be used for calculating age where birth date will be imputed as follows: 
 Any participant with a missing day will have this imputed as day ‘15’. Any participant with a missing day and month will have this imputed as ‘30th June’. Birth date will be presented in listings as ‘YYYY’.
Body Mass Index (BMI)

 Calculated as Weight (kg) / [Height (m)²]

11.5. Appendix 5: Reporting Standards for Missing Data

11.5.1. Premature Withdrawals

Element	Reporting Detail
General	
 Participant study completion (i.e., as specified in the protocol) was defined as the participant had completed all phases of the study including the final date on which data were or are expected to be collected. Withdrawn participants were not replaced in the study. All available data from participants who were withdrawn from the study will be listed and all available planned data will be included in summary tables and figures, unless otherwise specified.

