9.2. Sample Size Determination

As there is no formal research hypothesis being statistically tested in this study, the sample size was not selected based on statistical considerations but determined using feasibility. For each part, approximately 18 participants will be enrolled to ensure that 14 evaluable participants complete the study. If participants prematurely discontinue the study, additional participants may be enrolled after consultation with the sponsor to ensure that the required number of evaluable participants complete the study.

Note: "Enrolled" means a participant's, or their legally acceptable representative's, agreement has been obtained to participate in a clinical study following completion of the informed consent process and screening. Potential participants who are screened for the purpose of determining eligibility for the study, but do not participate in the study, are not considered enrolled, unless otherwise specified by the protocol.

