9.5. Interim Analysis

There will be no formal interim analysis. An analysis is planned after completion of Part 1 and will inform FDC formulation to include in Part 2. Preliminary safety & PK data will be analyzed by PPD under the oversight of Clinical Pharmacology Modeling & Simulation within VH/GSK.

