2.1. Changes to the Protocol Defined Statistical Analysis Plan

Changes from the originally planned statistical analysis specified in the protocol are outlined in Table 1.

Table 1 Changes to Protocol Defined Analysis Plan

Protocol	Reporting & Analysis Plan	
Statistical Analysis Plan	Statistical Analysis Plan	Rationale for Changes

 This is an open-label study 	
 Biostatistics and Programming teams from both GSK and PPD will remain blinded to the actual randomization schedule. Other teams including PPD Clinical Pharmacology team will remain open-label 	
 Biostatistics and Programming teams remain blinded following GSK's requirement

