3. PLANNED ANALYSES

3.1. Interim Analyses

There is no formal interim analysis planned but an analysis using preliminary PK data from Part 1 will be used to determine the formulation to be used for Part 2.

GSK Clinical Pharmacology Modeling and Simulation and the study team will inform the principal investigator of the formulation decision.

The interim outputs will be produced by WinNonlin (8.0 or higher).

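### Does the SAP's statement that withdrawals were not replaced conflict with the protocol's option to enrol more participants, and does it matter?

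*SAP*

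**What the plan says.** SAP 11.5.1, in the appendix on missing data, gives conventions for premature withdrawals. One bullet reads "Withdrawn participants were not replaced in the study". The next tells programmers to list whatever data withdrawn participants contributed and to carry their planned data into tables and figures.

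Protocol 9.2 takes a different line: "If participants prematurely discontinue the study, additional participants may be enrolled after consultation with the sponsor", the purpose being "to ensure that the required number of evaluable participants complete the study". SAP 2.5 repeats this word for word. The target behind it is "For each part, approximately 18 participants will be enrolled to ensure that 14 evaluable participants complete the study", and Protocol 9.2 says that "the sample size was not selected based on statistical considerations but determined using feasibility".

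SAP 2.1 states that "Changes from the originally planned statistical analysis specified in the protocol are outlined in Table 1". That table has one row, on keeping the biostatistics and programming teams blinded to the randomization schedule.

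On choosing the tablet for Part 2, Protocol 9.5 says "An analysis is planned after completion of Part 1 and will inform FDC formulation to include in Part 2", and SAP 3.1 says "an analysis using preliminary PK data from Part 1 will be used to determine the formulation to be used for Part 2". Neither mentions participants added to Part 1.

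**The concern.** A plan written before the data are in should not report as fact that nobody was replaced while two other sections keep that option open. On a first reading the sentence is either left over from a template or a quiet change of rule, and the SAP's table of changes does not help the reader decide. If anyone were added under Protocol 9.2, the statement would be false and could be copied into the study report.

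There is also a possible knock-on effect. The Part 1 data decide which tablet goes into Part 2. If Part 1 can be topped up, a reader may ask whether the formulation analysis waits for the extra participants. If no replacement were allowed, the evaluable number could fall below 14 and the confidence intervals would be wider than those tabulated in Protocol 9.2.1.

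**Working it through.** **1. The texts side by side.** Protocol 9.2 and SAP 2.5 give a permission, conditional on early discontinuation and on consulting the sponsor. SAP 11.5.1 makes an unconditional statement in the past tense. Both would be true if the option were never used. They collide only if someone is added. The bullet above it, on study completion, is also in the past tense although the SAP elsewhere looks ahead, which points to report-style template wording.

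**2. What depends on the sentence.**
- *Enrolment:* set by Protocol 9.2. A reporting convention in an SAP appendix does not control it.
- *Populations (SAP 4):* Safety requires at least one dose. The PK populations require sampling with evaluable results. An added participant qualifies on the same terms as anyone else.
- *Model (SAP 7.1.4.1):* treatment, period and sequence fixed, participant random. No term separates original from added participants.
- *Displays (SAP Appendix 9):* Tables 1.1 to 1.6 give enrolment, disposition, screening status and populations. Listings 1 to 4 give the randomization schedule and reasons for withdrawal. Actual conduct is reported from data.

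**3. Table 1.** Its stated scope is departures from the planned statistical analysis. Adding participants is study conduct, and SAP 2.5 restates the protocol rule, so the sample-size section contains no departure to declare.

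**4. Timing of the formulation analysis.** Protocol 4.4 defines completion for a participant and for the study. None of the sections quoted here defines completion of Part 1. The question of waiting for added participants comes from Protocol 9.2 and 9.5 alone and would remain if the 11.5.1 sentence were absent. The sponsor is consulted on any addition and also oversees the formulation analysis, so it can settle the timing when the case arises.

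**5. Size if the sentence were taken as a binding rule.**

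The allowance is 18 − 14 = 4 losses per part, or 4/18 = 22.2%. The documents give no dropout rate, so the rates below are assumptions. With independent losses, X ~ Binomial(18, p):

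| Assumed loss rate p | P(X > 4) |
|---|---|
| 5% | 0.0015 |
| 10% | 0.0282 |
| 15% | 0.1206 |
| 20% | 0.2836 |

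Protocol 7.2 expects withdrawals to be uncommon, which favours the upper rows.

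For precision, the half-width on the log scale is h = t(0.95, n−1) × √ln(1 + CVw²) × √(2/n). For GSK3640254, Protocol 9.2.1 takes CVw = 27.2%, so √ln(1 + 0.272²) = 0.2672. The n−1 degrees of freedom are inferred because they reproduce the protocol's table.

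| n | t × 0.2672 × √(2/n) | h | 90% CI at ratio 1.0 |
|---|---|---|---|
| 14 | 1.771 × 0.2672 × 0.3780 | 0.179 | 0.84–1.20 |
| 13 | 1.782 × 0.2672 × 0.3922 | 0.187 | 0.83–1.21 |
| 12 | 1.796 × 0.2672 × 0.4082 | 0.196 | 0.82–1.22 |

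The first row matches the protocol's 0.179 and 0.84–1.20. For DTG (CVw 21%) the same formula gives 0.139 at n = 14, again as tabulated, and 0.152 at n = 12.

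These figures bound what a strict no-replacement rule could cost. They are not a consequence of the sentence, because the protocol's permission stands.

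**The case for a change.** The best case for acting is that the clash is plain and costs almost nothing to remove. The rest of the SAP is prospective, so the sentence cannot be a report of what happened. The documents draw no line between an additional and a replacement participant, since the trigger is discontinuation and the aim is to restore the evaluable number. Table 1 already carries an operational item, so an operational departure could have been listed there. Losses may also cluster: Protocol 7.1.5 has the rest of a cohort discharged after a COVID-19 case, which makes the independent-loss probabilities optimistic and use of the Protocol 9.2 option more plausible.

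Part of this stands. SAP 11.5.1 and SAP 2.5 do not sit well together, and nothing in the documents reconciles them. Independence is an assumption, and evaluable numbers can also fall through the emesis and pre-dose concentration exclusions in SAP 7.1.1.2, which are not withdrawals. But clustered losses make it more likely that participants are added under Protocol 9.2. They do not give the SAP sentence any power to prevent that, or to alter how the added participants are analysed. An untrue statement would reach the report only if someone copied it against the study's own disposition tables.

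**Conclusion.** This is a clerical slip: one sentence in a reporting appendix that does not fit the SAP's own sample-size section or the protocol. It changes no enrolment decision, estimate, interval or display, so no change to the plan is called for. The lack of a stated rule on whether the formulation analysis waits for added Part 1 participants is a separate, minor gap that the sponsor can fill when needed. The silence of Table 1 is consistent with its scope.

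The conclusion rests on Protocol 9.2 governing enrolment, on SAP 2.5 agreeing with it, and on populations and models that treat every dosed and sampled participant alike. It does not rest on any dropout rate. Even if the sentence were enforced, falling to 12 evaluable would add 0.196 − 0.179 = 0.017 to the GSK3640254 log half-width. The study tests no hypothesis, and its sample size was set by feasibility.
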